### 6.9 Dose Modification and Dose Delays

The treatment management guidelines including dose delay and dose modification of TJ004309 for hematological and non-hematological toxicities are provided in [Table 6](#) and [Table 7](#) respectively. Treatment management guidelines for Immune-Related Adverse Events (irAEs) are provided in [Table 8](#).

Dose delay up to 4 weeks is allowed for subjects with manageable AEs at the Investigator's discretion, e.g., Grade 4 or Grade 3 thrombocytopenia with Grade  $\geq 2$  bleeding, uncomplicated Grade 3 febrile neutropenia, and Grade 4 neutropenia. The Investigator can continue to withhold treatment for up to 12 weeks after the last dose based on the Investigator's medical judgement. If the subject has recovered to Grade  $\leq 1$  or baseline within 12 weeks, continue treatment of TJ004309 at the same dose level. Dose modification or withholding of doses other than as described in this section is not permitted.

If a Grade  $\geq 2$  toxicity recurs for the second time, the Investigator may discuss with the Sponsor whether resuming TJ004309 is appropriate considering the type and grade of the toxicity. If the agreement is to resume TJ004309, treatment can continue to be withheld for up to 12 weeks to allow the subject to recover to Grade  $\leq 1$  or baseline at the Investigator's discretion. If the subject recovers to Grade  $\leq 1$  or baseline within 12 weeks, continue treatment of TJ004309 at the same dose level. If the subject does not recover within 12 weeks, permanently discontinue TJ004309. The Investigator should always manage their subjects according to their medical judgment based on the clinical circumstances.

All dose modifications must be clearly documented in the subjects' source notes and Case Report Form (CRF).

Study treatment dose delays are permitted in the case of medical/surgical events or logistical reasons not related to study therapy (e.g., surgery, unrelated medical events, patient vacation, and/or holidays). Participants should be placed back on study therapy within 28 days of the scheduled interruption, unless otherwise discussed with the Sponsor. The reason for interruption should be documented in the patient's study record. All dose delays must be clearly documented in the patients' source notes and the eCRF.

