**Table 6: TJ004309 Treatment Management Guidelines for Adverse Events (Hematological Toxicities)**

Adverse Event	Grade	Management Actions*
Neutropenia	Grade $\geq 4$	
 
If the subject has recovered to Grade <math>\leq 1</math> or baseline within 4 weeks, continue treatment of TJ004309 at the same dose level. If the subject has not recovered within 4 weeks, the Investigator can continue to withhold for up to 12 weeks after the last dose based on the Investigator's medical judgement.
 
Monitor absolute neutrophil count weekly until recovered or stable.
 
Conduct adequate evaluation to confirm etiology and/or exclude other causes.
 
Initiate broad spectrum antibiotics.
 
Consider initiating Granulocyte-colony stimulating factor (G-CSF) such as filgrastim or pegylated filgrastim.
 
If the event recurs for the second time, withhold treatment for up to 12 weeks while giving appropriate medical treatment at the Investigator's discretion. If the subject has recovered to Grade <math>\leq 1</math> or baseline within 12 weeks, continue treatment of TJ004309 at the same dose level. If the subject has not recovered within 12 weeks, permanently discontinue TJ004309.
 

Febrile Neutropenia	Grade $\geq 3$	See above
Other hematological toxicities 	Grade $\geq 3$	
 
If the subject has recovered to Grade <math>\leq 1</math> or baseline within 4 weeks, continue treatment of TJ004309 at the same dose level. If the subject has not recovered within 4 weeks, the Investigator can continue to withhold for up to 12 weeks after the last dose based on the Investigator's medical judgement.
 
Monitor hematological toxicities weekly until recovered or stable.
 
Conduct adequate evaluation to confirm etiology and/or exclude other causes.
 
If the event recurs for the second time, withhold treatment for up to 12 weeks while giving appropriate medical treatment at the Investigator's discretion. If the subject has recovered to Grade <math>\leq 1</math> or baseline within 12 weeks, continue treatment of TJ004309 at the same dose level. If the subject has not recovered within 12 weeks, permanently discontinue TJ004309.
 

 With the exception of Grade 3 or 4 lymphopenia.

\*Treating physicians' assessment and judgement are critical, and all the management actions should be taken with physician's discretion

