**Table 8: TJ004309 Treatment Management Guidelines for Immune-Related Adverse Events (irAEs)**

General instructions:

1. Severe and life-threatening irAEs should be treated with IV corticosteroid followed by oral steroids. Other immunosuppressive treatment should begin if the irAEs are not controlled by corticosteroids.
2. TJ004309 must be permanently discontinued if the irAE does not resolve or the corticosteroid dose is not  $\leq 10$  mg/day within 12 weeks of the last treatment.
3. The corticosteroid taper should begin when the irAE is  $\leq$  Grade 1 and continue tapering at least 4 weeks.
4. If TJ004309 has been withheld, TJ004309 may resume after the irAE decreased to  $\leq$  Grade 1 after corticosteroid taper.

irAEs	Toxicity Grade (CTCAE V5.0)	Action with TJ004309	Corticosteroid and/or other therapies	Monitoring and Follow-up
Pneumonitis	Grade 2	Withhold	Administer corticosteroids (initial dose of 1 to 2 mg/kg prednisone or equivalent) followed by taper Add prophylactic antibiotics for opportunistic infections	Monitor participants for signs and symptoms of pneumonitis Evaluate participants with suspected pneumonitis with radiographic imaging and initiate corticosteroid treatment
	Recurrent Grade 2, Grade 3 or 4	Permanently discontinue		
Diarrhea / Colitis	Grade 2 or 3	Withhold	Administer corticosteroids (initial dose of 1 to 2 mg/kg prednisone or equivalent) followed by taper	Monitor participants for signs and symptoms of enterocolitis (ie, diarrhea, abdominal pain, blood or mucus in stool with or without fever) and of bowel perforation (ie, peritoneal signs and ileus) Participants with $\geq$ Grade 2 diarrhea suspecting colitis should consider GI consultation and performing endoscopy to rule out colitis Participants with diarrhea/colitis should be advised to drink liberal quantities of clear fluids. If sufficient oral fluid intake is not feasible, fluid and electrolytes should be substituted via IV infusion
	Recurrent Grade 3 or Grade 4	Permanently discontinue		
AST or ALT elevation or Increased Bilirubin	Grade 2 a	Withhold	Administer corticosteroids (initial dose of 0.5 to 1 mg/kg prednisone or equivalent) followed by taper	Monitor with liver function tests (consider weekly or more frequently until liver enzyme value returned to baseline or is stable)

	Grade 3 b or 4 c	Permanently discontinue	Administer corticosteroids (initial dose of 1 to 2 mg/kg prednisone or equivalent) followed by taper	

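### Section 6.9 permits same-dose TJ004309 after a recurrent Grade ≥ 2 toxicity and makes no exception for events that Tables 7 and 8 say must end treatment on recurrence

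*Protocol*

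**What the plan says.** The opening of Protocol Section 6.9 sends hematological and non-hematological toxicities to Tables 6 and 7, and immune-related events to Table 8: "Treatment management guidelines for Immune-Related Adverse Events (irAEs) are provided in" that table. It states no order of precedence between the section text and the tables.

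A later paragraph of Section 6.9 deals with recurrence at Grade 2 or higher. It applies when such an event "recurs for the second time, the Investigator may discuss with the Sponsor whether resuming TJ004309 is appropriate considering the type and grade of the toxicity". The two parties may then settle on restarting, and for that case the paragraph provides: "If the agreement is to resume TJ004309, treatment can continue to be withheld for up to 12 weeks to allow the subject to recover". Recovery here means a return to baseline or to no worse than Grade 1. If recovery comes in time, the instruction is to "continue treatment of TJ004309 at the same dose level. If the subject does not recover within 12 weeks", TJ004309 stops for good. The paragraph closes by deferring to the Investigator's medical judgment, not to any table.

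Table 8 requires permanent discontinuation for these recurrences:

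- Pneumonitis: "Recurrent Grade 2, Grade 3 or 4".
- Diarrhea/colitis, and separately the row for all other irAEs: "Recurrent Grade 3 or Grade 4".

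In Table 7, the diarrhea/colitis row also ends treatment permanently on a recurrent Grade ≥ 3 event.

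**The concern.** The paragraph and the table rows can give different answers for the same patient. Suppose a patient has a second Grade 2 pneumonitis that resolves in four weeks. Under Table 8 that patient is permanently off TJ004309. Under the Section 6.9 paragraph, on the second-episode reading, the Investigator and Sponsor may agree to give 20 mg/kg again.

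What is at stake is safety after a recurrent immune-related event in patients who also receive a PD-L1 antibody. A site that re-dosed could cite Section 6.9, and no sentence in the protocol says that the table should have governed.

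**Working it through.** No arithmetic beyond counting applies. The check sets the texts side by side.

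**1. The two rules for the same event**

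| Recurrent event | Table action | Section 6.9 recurrence paragraph |
|---|---|---|
| Grade 2 pneumonitis (Table 8) | Permanent stop | Same-dose restart possible by agreement |
| Grade 3 diarrhea/colitis (Table 8) | Permanent stop | Same |
| Grade 3, all other irAEs (Table 8) | Permanent stop | Same |
| Grade ≥ 3 diarrhea/colitis (Table 7) | Permanent stop, under that table's discretion footnote | Same |

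In each table row the stop applies whether or not the patient recovers. In the Section 6.9 paragraph the only mandatory stop is failure to recover within 12 weeks.

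**2. Does Table 8 contain its own release?** General instruction 4 begins "If TJ004309 has been withheld, TJ004309 may resume after the irAE decreased to" Grade 1 or lower, so it reaches a drug that was withheld, not one permanently discontinued. Footnote d gives discretion, but it is attached to the diabetes/hyperglycemia, hypophysitis and hyperthyroidism rows. The withhold-or-discontinue option with footnote e belongs to the Grade 3 row for other irAEs, not to the recurrence row below it. Tables 6 and 7 carry a table-wide note on physician's discretion and Table 8 does not, so its recurrence rows read as mandatory.

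**3. Does the Grade ≥ 2 trigger confine the paragraph to Tables 6 and 7?** Counting the event types for which Grade 2 is a listed grade:

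- Table 6: 0 of 3
- Table 7: 2 of 5 (infusion reactions, diarrhea/colitis)
- Table 8: 10 of 12 (all except diabetes/hyperglycemia and exfoliative skin conditions)

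The trigger grade therefore does not exclude Table 8.

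**4. Which episode is meant?** Table 6 uses the same phrase after its opening recovery rule: "If the event recurs for the second time, withhold treatment for up to 12 weeks while giving appropriate medical treatment".

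- *Second episode.* If the opening rule is for the first event, the phrase means the second episode, and all four entries in the table above conflict with Section 6.9.
- *Third episode.* The tables would usually have ended treatment one episode earlier, so little conflict remains. One example that survives is colitis at Grade 3, then Grade 2 (withhold only), then Grade 3. Table 8 stops at the third episode, where Section 6.9 would allow a restart.

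**5. How many rows?** Table 8 has eight irAE types with a mandatory permanent stop: pneumonitis, diarrhea/colitis, AST/ALT/bilirubin, nephritis, neurological, myocarditis, confirmed SJS/TEN/DRESS and all other irAEs. Three of the eight name recurrence as a trigger. With the Table 7 row, 3 + 1 = 4 entries tie a permanent stop to recurrence at a stated grade.

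**6. How often?** The documents give no rate of recurrent irAEs. Protocol Table 4 (Phase 1, N = 20) lists nothing above Grade 2, but it is limited to events in more than one patient and does not report recurrence. It does not bound the rate.

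**The case against.** The strongest reply is that there is no true contradiction. Section 6.9 only lets the parties discuss whether restarting is appropriate, it requires Sponsor agreement, and it tells them to consider type and grade, which is how Table 8 is organised. Where a row says to stop permanently, the natural outcome is not to restart. The paragraph's vocabulary also follows Tables 6 and 7: the second-time phrase, the 12-week hold and the unchanged dose level. Table 8 has its own resume and 12-week instructions, and a specific row would ordinarily govern over general text.

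Much of this stands. The specific-over-general reading is sensible and probably intended. A reader might infer that the protocol directs re-dosing after recurrent pneumonitis or colitis, or that a site cannot obey both texts. The documents support neither inference, because the paragraph is permissive and following the tables satisfies both. What remains is that the precedence is not written, and considering type and grade allows the parties to decline without requiring them to.

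The episode count is also open to challenge. Taken literally, recurring for the second time is the third episode, and the opening rule in Table 6 is not expressly limited to a first event. That is a fair reading and the text does not settle it, so the point has to be stated under both.

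**Conclusion.** The concern holds as a modest patient-safety inconsistency. Section 6.9 gives written permission, by agreement, for same-dose resumption after recurrence. It does not except the three Table 8 recurrence rows or the Table 7 diarrhea/colitis row, and nothing says the tables prevail. The Table 7 conflict is the weaker one because that table already allows physician's discretion.

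The size depends on one assumption. If the phrase means the second episode, the conflict is direct for all four entries. If it means the third, only unusual sequences are affected.

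A reader might also infer a threat to the efficacy result. The documents do not support that: no SAP definition or method turns on which text governs, and no effect on ORR or any other SAP output is shown. SAP Section 4.1 states that Part 2 was not initiated, so the practical reach is any Part 1 patient still on treatment and any later protocol that reuses this text.

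**What to change.** Add one sentence to the recurrence paragraph of Section 6.9:

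> *This paragraph does not apply to any event for which Table 7 or Table 8 requires permanent discontinuation of TJ004309; in that case the table prevails.*

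The sentence works whether the second or the third episode is meant. It also covers a Grade 2 event that returns at a grade for which Table 8 requires a permanent stop at any occurrence, such as Grade 3 nephritis. Naming Table 7 matters, because a sentence limited to Table 8 would leave the diarrhea/colitis row there in conflict. The tables need no edits, and Table 7's discretion footnote stays as it is.

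The cost is one sentence in a protocol amendment and slightly less discretion to re-dose after such events. Data collection, sample size and analysis are unchanged.

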**Table 6: TJ004309 Treatment Management Guidelines for Adverse Events (Hematological Toxicities)**

Adverse Event	Grade	Management Actions*
Neutropenia	Grade $\geq 4$	
 
If the subject has recovered to Grade <math>\leq 1</math> or baseline within 4 weeks, continue treatment of TJ004309 at the same dose level. If the subject has not recovered within 4 weeks, the Investigator can continue to withhold for up to 12 weeks after the last dose based on the Investigator's medical judgement.
 
Monitor absolute neutrophil count weekly until recovered or stable.
 
Conduct adequate evaluation to confirm etiology and/or exclude other causes.
 
Initiate broad spectrum antibiotics.
 
Consider initiating Granulocyte-colony stimulating factor (G-CSF) such as filgrastim or pegylated filgrastim.
 
If the event recurs for the second time, withhold treatment for up to 12 weeks while giving appropriate medical treatment at the Investigator's discretion. If the subject has recovered to Grade <math>\leq 1</math> or baseline within 12 weeks, continue treatment of TJ004309 at the same dose level. If the subject has not recovered within 12 weeks, permanently discontinue TJ004309.
 

Febrile Neutropenia	Grade $\geq 3$	See above
Other hematological toxicities 	Grade $\geq 3$	
 
If the subject has recovered to Grade <math>\leq 1</math> or baseline within 4 weeks, continue treatment of TJ004309 at the same dose level. If the subject has not recovered within 4 weeks, the Investigator can continue to withhold for up to 12 weeks after the last dose based on the Investigator's medical judgement.
 
Monitor hematological toxicities weekly until recovered or stable.
 
Conduct adequate evaluation to confirm etiology and/or exclude other causes.
 
If the event recurs for the second time, withhold treatment for up to 12 weeks while giving appropriate medical treatment at the Investigator's discretion. If the subject has recovered to Grade <math>\leq 1</math> or baseline within 12 weeks, continue treatment of TJ004309 at the same dose level. If the subject has not recovered within 12 weeks, permanently discontinue TJ004309.
 

 With the exception of Grade 3 or 4 lymphopenia.

\*Treating physicians' assessment and judgement are critical, and all the management actions should be taken with physician's discretion

**Table 7: TJ004309 Treatment Management Guidelines for Adverse Events (Non-Hematological Toxicities)**

Adverse Event	Grade	Management Actions*
Infusion Related Reactions (IRR) 	Grade 2	
 
Interrupt or slow the rate of infusion. Monitor and if the reaction worsens, stop infusion.
 
Administer institutional standard medications for hypersensitivity reaction as medically indicated. Monitor symptoms until stable. Re-initiate infusion if patient is stable at a 50% slower rate. Prophylactic medications indicated for <math>\leq</math> 24 hours.
 
For subsequent infusions, administer premedication with the following or per institutional standard:           
 
H-1 antihistamine: Diphenhydramine 25-50 mg PO or IV 30 minutes prior to infusion
 
Acetaminophen 500-1000 mg PO 30 minutes prior to infusion
 
Corticosteroids such as dexamethasone (or equivalent) or anti- emetics such as ondansetron (or equivalent) may be administered based on clinical presentation of previous IRR
 
 
 
For subsequent infusions, may administer TJ004309 at a 50% slower rate.
 

	Grade $\geq$ 3	
 
Stop infusion immediately and discontinue TJ004309.
 
Administer epinephrine, bronchodilators, antihistamines, glucocorticoids, IV fluids, vasopressors, oxygen, etc. as medically indicated. Contact sponsor to report SAE.
 
Increase monitoring of vital signs as medically indicated until stable.
 

Chills	Grade 3	
 
Stop the infusion.
 
Administer aggressive symptomatic therapy per institutional standard.
 
After resolution of all symptoms, treatment can be resumed at slower rate, unless severe reaction. If severe reaction, then withhold TJ004309 per Investigator's discretion of clinical presentation of the subject.
 

Diarrhea/Colitis	Grade 2 or 3 that persists for $\geq 7$ days despite adequate steroid therapy	
 
• Withhold.
 
• Should consult with gastroenterology for Grade <math>\geq 2</math>.
 
• Administer corticosteroids starting with initial dose of 1- 2 mg/kg/day prednisone or equivalent. Consider hospitalization or outpatient facility for patients with dehydration or electrolyte imbalance. When symptoms improve to Grade <math>\leq 1</math>, taper corticosteroids over at least 4 - 6 weeks before resuming treatment, although resuming treatment while on low-dose corticosteroid may also be an option after an evaluation of the risks and benefits.
 
• Monitor subject for signs and symptoms of enterocolitis and/or bowel perforation and advise patient to increase oral fluids or IV infusion if needed.
 
• If the subject has recovered to Grade <math>\leq 1</math> or baseline within 4 weeks, and treatment is restarted during corticosteroid taper, continue treatment of TJ004309 at the same dose level. If the subject has not recovered within 4 weeks, the Investigator can continue to withhold for up to 12 weeks after the last dose based on the Investigator's medical judgement.
 
• If recurrent Grade <math>\geq 3</math> permanently discontinue TJ004309.
 

Nausea, vomiting, fatigue, or electrolyte abnormalities	Grade 3 if persisting despite optimal medical treatment	
 
• If the subject has recovered to Grade <math>\leq 1</math> or baseline within 4 weeks, continue treatment of TJ004309 at the same dose level. If the subject has not recovered within 4 weeks, the Investigator can continue to withhold for up to 12 weeks after the last dose based on the Investigator's medical judgement.
 
• Monitor toxicities weekly until recovered or stable.
 
• Give supportive care based on Investigator discretion.
 
• Conduct adequate evaluation to confirm etiology and/or exclude other causes.
 
• If recurs for the second time, withhold treatment for up to 12 weeks while giving appropriate medical treatment at the Investigator's discretion. If the subject has recovered to Grade <math>\leq 1</math> or baseline within 12 weeks, continue treatment of TJ004309 at the same dose level. If the subject has not recovered up to 12 weeks, permanently discontinue TJ004309.
 

	Grade 4	
 
Give supportive care based on Investigator discretion.
 
If the subject has recovered to Grade <math>\leq 1</math> or baseline within 4 weeks, continue treatment of TJ004309 at the same dose level. If the subject has not recovered within 4 weeks, the Investigator can continue to withhold for up to 12 weeks after the last dose based on the Investigator's medical judgement.
 
If recurs for the second time, withhold treatment for up to 12 weeks while giving appropriate medical treatment at the Investigator's discretion. If the subject has recovered to Grade <math>\leq 1</math> or baseline within 12 weeks, continue treatment of TJ004309 at the same dose level. If the subject has not recovered up to 12 weeks, permanently discontinue TJ004309.
 

Other non-hematological adverse reactions	Grade 3	
 
If the subject has recovered to Grade <math>\leq 1</math> or baseline within 4 weeks, continue treatment of TJ004309 at the same dose level. If the subject has not recovered within 4 weeks, the Investigator can continue to withhold for up to 12 weeks after the last dose based on the Investigator's medical judgement.
 
Monitor toxicities weekly until recovered or stable.
 
Give supportive care based on Investigator discretion.
 
Conduct adequate evaluation to confirm etiology and/or exclude other causes.
 
If recurs for the second time, withhold treatment for up to 12 weeks while giving appropriate medical treatment at the Investigator's discretion. If the subject has recovered to Grade <math>\leq 1</math> or baseline within 12 weeks, continue treatment of TJ004309 at the same dose level. If the subject has not recovered up to 12 weeks, permanently discontinue TJ004309.
 

	Grade 4	
 
Discontinue TJ004309.
 

For further information, please refer to the Common Terminology Criteria for Adverse Events v5.0 (CTCAE) at <http://ctep.cancer.gov>

\*Treating physicians' assessment and judgement are critical, and all the management actions should be taken with physician's discretion.

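### Table 7's diarrhea/colitis row starts steroids only after steroids have failed and withholds later than Table 8, and no sentence says which table governs a suspected or undetermined case (small impact)

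*Protocol*

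**What the plan says.** Protocol section 6.9 refers non-hematological toxicities to Table 7 and immune-related adverse events (irAEs) to Table 8. Both tables have a diarrhea/colitis row.

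**Table 7.** The row is entered at Grade 2 or 3 persisting for at least 7 "days despite adequate steroid therapy". Its actions include withholding TJ004309 and: "Administer corticosteroids starting with initial dose of 1- 2 mg/kg/day prednisone or equivalent". On restart, once symptoms reach Grade 1 or lower, sites are to "taper corticosteroids over at least 4 - 6 weeks before resuming treatment". That is the default. The same sentence then offers an exception: "although resuming treatment while on low-dose corticosteroid may also be an option after an evaluation of the risks and benefits". A later bullet keeps the same dose level if the patient recovers within 4 weeks and "treatment is restarted during corticosteroid taper".

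**Table 8.** The row withholds at Grade 2 or 3, with no duration or steroid-failure condition, and starts steroids at 1 to 2 mg/kg. General instruction 3 begins the taper at Grade 1 or lower "and continue tapering at least 4 weeks". General instruction 4 says "If TJ004309 has been withheld, TJ004309 may resume after the irAE decreased to" Grade 1 or lower after the taper. General instruction 2 says "TJ004309 must be permanently discontinued if the irAE does not resolve or the corticosteroid dose is not" at or below 10 mg/day within 12 weeks of the last treatment.

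**Section 6.8.1.** Prednisone at 10 mg/day or more for supportive care is prohibited. Acute use for a suspected irAE is excepted, but the systemic steroid should then be stopped at least 24 hours before the next study dose.

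**Discretion.** Section 6.9 allows dose delay of up to 4 weeks at the Investigator's discretion for manageable events, and the Table 7 footnote leaves all actions to the physician. Section 6.9 also bars withholding other than as it describes.

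**The concern.** Diarrhea on a checkpoint-inhibitor combination may have no settled cause when it presents. At that moment a site needs one rule for withholding and one for restarting. A site that opens Table 7 finds a row that names colitis, presupposes steroids and monitors for enterocolitis and perforation, so it does not read as a row for non-immune diarrhea only. Its trigger comes later than Table 8's, and its steroid step does not fit a patient who has met that trigger. Two sites could therefore follow different written rules for the same Grade 2 or 3 event. What is at stake is patient safety and uniform conduct, not an efficacy estimate.

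**Working it through.** The plan states no figure on this point, so there is none to reproduce. The check sets the texts side by side and then sizes the consequence.

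**Step 1: compare the rules.**

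| Item | Table 7 | Table 8 | Section 6.8.1 |
|---|---|---|---|
| Withhold at | Grade 2 or 3 for 7 days or more despite adequate steroids | Any Grade 2 or 3 | Not addressed |
| Steroid step | Initial 1 to 2 mg/kg/day | Initial 1 to 2 mg/kg | Acute use allowed for suspected irAE |
| If steroids fail | No further agent named | Other immunosuppression (general instruction 1) | Not addressed |
| Restart | Default: taper at least 4 to 6 weeks, then resume. Exception: on low-dose steroid, undefined | Grade 1 or lower, after a taper of at least 4 weeks | Steroid stopped at least 24 hours before dosing |

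- Trigger against action: the trigger requires failed steroids and the action is a first dose of steroids. The two do not fit.
- Table 7 against Table 8: the withhold triggers differ for the same named event.
- Governing sentence: section 6.9 sends irAEs to Table 8, and the Table 8 note leaves non-irAEs to clinical practice. Table 8's wording on suspected colitis covers consultation and endoscopy, not dosing. Nothing assigns a suspected or undetermined case.
- Restart against section 6.8.1: resuming during a taper at prednisone 10 mg/day or more, given for a suspected irAE, breaks the 24-hour rule. Below 10 mg/day the texts are ambiguous. The rule sits inside a bullet prohibiting 10 mg/day or more, but the 24-hour sentence gives no dose floor of its own.

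**Step 2: how often.** Inputs: Protocol Table 4 (N = 20, suspected related to TJ004309) gives diarrhea Grade 1 in 4, Grade 2 in 1 and Grade 3 or higher in 0. Section 4.1 allows up to 30 per cohort, so up to 60 in Part 1. Intervals are exact Clopper-Pearson 95%.

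- Grade 2: 1/20 = 5.0% (0.1% to 24.9%). Scaled to 60: 60 × 0.05 = 3.0 expected; upper limit 60 × 0.2487 = 14.9.
- Grade 3 or higher: 0/20 (0% to 16.8%). Scaled to 60: 0 expected; upper limit 60 × 0.1684 = 10.1.
- Chance of at least one Grade 2 case in 60 at a 5% rate: 1 − 0.95^60 = 0.954.

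**Step 3: how often the trigger gap meets a dosing day.** An initial 1 to 2 mg/kg exceeds 10 mg/day in any adult, so section 6.8.1 already limits dosing once steroids for a suspected irAE begin. The exposed time is the days before that. Assumptions not in the documents: a lag of 0 to 3 days and onset uniform over the 21-day cycle.

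- Chance a dose falls due in the lag: 0/21 = 0% to 3/21 = 14.3%.
- Patients among 60 at the Grade 2 rate: 0 to 3.0 × 3/21 = 0.43; at its upper limit, 0 to 14.9 × 3/21 = 2.13.
- These count every related Grade 2 event. If 25% to 50% have undetermined cause (assumption), the maxima become 0.11 to 0.21, or 0.53 to 1.07 at the upper limit.

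**Step 4: restart timing.** Table 8's minimum taper is 28 days, and Table 7's exception has no minimum. 28/21 = 1.33, so sites could differ by 1 or 2 doses if the exception is used. If steroids must stop before dosing, the exception falls away and Table 7's default is at least as long as Table 8's.

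**The case against.** The strongest reply is that the gap is narrow. A diagnosed irAE goes to Table 8. Section 6.8.1 already speaks of suspected irAEs, so a patient on steroids for suspected immune diarrhea is constrained before Table 7's 7-day condition is met. Investigators may delay doses at their discretion. This stands, and it is why the impact is small. It does not remove the fault, because section 6.9 also bars withholding other than as described, so the described rules need to agree.

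Three stronger readings are tempting, and the documents do not support them.

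- *The row contradicts itself on restart.* It does not. It gives a default and a labelled exception, and the later bullet supplies the dose level for that exception. The fault is that low-dose is undefined.
- *Any restart on steroid breaks section 6.8.1.* The conflict is clear only at prednisone 10 mg/day or more for a suspected irAE. Table 8's general instruction 2 also tolerates a residual dose at or below 10 mg/day.
- *Table 7 tells sites to keep dosing until day 7.* It gives no instruction before its trigger.

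It is also fair to object that the Phase 1 rate pools weekly and three-weekly schedules from 5 to 20 mg/kg and counts only events attributed to TJ004309. Table 4 shows only terms seen in more than one patient, so a single colitis case would not appear. The interval is wide for these 20 patients, and it does not cover those differences.

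**Conclusion.** The point holds as a minor fault in patient-safety wording. Three things are wrong as written: a steroid-failure trigger paired with a first-steroid action, a later withhold trigger than Table 8's, and no sentence governing suspected or undetermined cases. Two narrower faults attach to restart: low-dose is undefined, and restart at prednisone 10 mg/day or more for a suspected irAE conflicts with section 6.8.1.

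The best estimate is about 3 Grade 2 events among 60 patients (interval about 0 to 15), with a dose falling in the unprotected days for 0 to 0.4 patients, or up to 2.1 at the upper limit. These figures assume that the Phase 1 rate carries over, and rest on the stated lag and uniform onset.

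A reader might infer that efficacy results are affected. They are not: no endpoint or analysis depends on these rows. SAP section 4.1 records that Part 2 was not initiated, and SAP section 1 plans an abbreviated report. The documents do not show whether anyone is still on treatment, so the correction matters for any remaining patients and for any later protocol that reuses the tables.

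**What to change.** 1. State in section 6.9 that Table 8 governs any suspected immune-related or undetermined diarrhea/colitis: withhold at Grade 2 or 3, and resume at Grade 1 or lower after the taper.
2. Limit the Table 7 row to diarrhea judged non-immune. Replace its trigger with Grade 2 or 3 persisting despite optimal supportive treatment, and remove its steroid and restart-on-steroid wording. Keeping the row is better than deleting it, because the catch-all row for other non-hematological reactions starts at Grade 3 and would leave non-immune Grade 2 diarrhea without a row.
3. Apply one restart steroid rule in Table 8 and section 6.8.1: either steroids stopped at least 24 hours before dosing, or a stated ceiling below 10 mg/day prednisone. This also settles the boundary at exactly 10 mg/day, which section 6.8.1 prohibits for supportive care and Table 8's general instruction 2 accepts.

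The cost is amendment wording: one table row, one sentence in section 6.9 and one aligned restart rule. The downside is a few extra withheld doses for diarrhea that proves non-immune.
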